9. STATISTICAL METHODS

9.1 STATISTICAL ANALYSIS

All statistical analyses will be performed by SGS Life Science Services using SAS® (SAS Institute Inc., Cary, NC, USA; version 9.2 or higher) software for statistical computations.

All statistical methods shall be detailed in a Statistical Analysis Plan (SAP) that will be finalized before database lock.

All data collected in this study will be documented using summary tables, figures, and subject data listings.

Descriptive statistics will include number of subjects, (arithmetic) mean, standard deviation (SD), median, minimum and maximum, and a 95% confidence interval (CI). Frequency tabulations will show counts and percentages.

All statistical tests will be interpreted at the 5% significance level (2-tailed).

An interim analysis on the primary endpoint, DEXA parameters and safety data will be performed once the first 16 subjects will have completed 12 weeks of treatment and the follow-up visit (or have discontinued earlier). The final analysis will be performed once all subjects will have completed 12 weeks of treatment and the follow-up visit (or have discontinued earlier).

The following populations will be considered for analysis:

- Safety population: defined as all subjects who are randomized into the study and received at least one dose of the study drug. All safety tables and listings will be based on the safety population.
- Intent-to-treat (ITT) population: defined as all randomized subjects who received at least one dose of the study drug and who have post-baseline efficacy data. Unless specified otherwise, the ITT population will be used for efficacy analysis.
- Per-protocol (PP) population: defined as a subset of the ITT population, excluding those subjects who have major protocol deviations and violations. All deviations and violations will be reviewed prior to database lock and classified as either minor or major.

9.1.1 Initial Characteristics of the Subject Sample

Demographic data (age, race, body weight, height and Body Mass Index [BMI]) will be summarized. Demographic data will be presented for the safety population. In case the ITT and/or PP population(s) deviate by more than 5% from the safety population, demographic data will also be presented for the ITT and/or PP population(s). The evaluation consists of descriptive statistics and frequency tabulations, as appropriate.

Subject disposition data such as study termination reasons, visit adherence, and compliance to ePRO completion will be tabulated.

Demographic data and disposition data will be presented overall and per treatment arm.

Findings for medical and surgical history and concomitant diseases will be tabulated per treatment arm.

The use of study drugs will be summarized by treatment arm.

Prior and concomitant medications will be coded using the World Health Organization (WHO)_DRUG dictionary and will be summarized.

Protocol deviations will be tabulated.

9.1.2 *Pharmacokinetic Data*

Individual plasma ESN364 concentration values and actual sampling times relative to study drug intake will be listed. Descriptive statistics will be summarized by assessment time point.

9.1.3 *Pharmacodynamic Data*

Individual plasma hormone concentration values and actual sampling times relative to study drug intake will be listed. Descriptive statistics on the actual values and changes from baseline values will be summarized by assessment time point and by treatment arm.

9.1.4 *Efficacy Data*

For a list of efficacy endpoints, see Sections [7.4.2](#).

Primary Endpoint

Changes from baseline in Hot Flash Score will be analyzed using an Analysis of Covariance (ANCOVA) model with treatment as fixed effect and baseline as covariate. If a significant difference between the treatment arms is present, differences between each active treatment arm and placebo will be tested, correcting for multiplicity.

Rules for defining valid diary days and imputing missing scores will be elaborated in the SAP.

Secondary Endpoints

Hot Flash Score and Hot Flash Frequency at all time points will be evaluated by means of descriptive statistics (actual values and changes from baseline) by treatment arm.

The percentage of subjects with at least 70% reduction from baseline in Hot Flash Score will be compared across the treatment arms, using chi-square or Fisher exact test, as appropriate.

The percentage of subjects with at least 50% reduction in the number of moderate and severe hot flashes will be compared across the treatment arms, using chi-square or Fisher exact test, as appropriate.

Questionnaires will be evaluated by means of descriptive statistics (actual values and changes from baseline) by treatment arm. HFRDIS, GCS, SDS and LSEQ total scores and subscores (if applicable) are to be reported.

Change in lean body mass, fat mass, and bone mass/density will be explored by means of descriptive statistics on the actual values, at each assessment time point and by treatment arm. Changes from baseline to Week 12 will be summarized by treatment arm.

9.1.5 Safety Data

Safety parameters will be tabulated and analyzed descriptively.

Adverse Events

The original terms used in the source documents and the designated sections of the eCRFs by the Investigator to identify AEs will be fully described and coded according to the Medical Dictionary for Regulatory Activities (MedDRA).

The reported AEs will be allocated to phases based on their start date. All AEs will be listed. All AEs with onset during the treatment phase (i.e., TEAEs) will be summarized by treatment arm by System Organ Class (SOC) and Preferred Term (PT).

Special attention will be paid to those subjects who died, discontinued the study drug due to an AE, or experienced a severe or serious AE. Summaries, listings, and narratives (also see Section 12.11) may be provided, as appropriate.

Clinical Laboratory Tests

Each continuous biochemistry and hematology laboratory test will be evaluated by means of descriptive statistics on the actual values, at each assessment time point and by treatment arm. Changes from baseline will be summarized by assessment time point and by treatment arm.

Laboratory tests will be categorized according to the normal ranges of the clinical laboratory (below, within, or above normal). A shift table versus baseline will be created. The worst post-baseline value will be summarized as well.

A listing of subjects with any clinical laboratory test result outside the normal range of the clinical laboratory will be provided.

Vital Signs

Body temperature, pulse rate, SBP, and DBP will be evaluated by means of descriptive statistics (actual values and changes from baseline) and shift tables according to the normal ranges (as defined in [Attachment 7](#)) at each assessment time point and by treatment arm.

Electrocardiogram

Electrocardiogram variables will be evaluated by means of descriptive statistics (actual values and changes from baseline) and shift tables according to the normal ranges (as defined in [Attachment 7](#)) at each assessment time point and by treatment arm.

The ECG variables that will be analyzed are HR, PR interval, QRS interval, QT interval. Values for QTc will be derived. QTcF will be the primary correction parameter [\[31\]](#). Categorical assessment will be performed on absolute QTcF interval prolongation (>450, >480, >500 ms) and on changes from baseline (increase >30 and >60 ms).

Physical Examination

Abnormal findings in physical examination will be listed.

9.1.6 *Interim Analysis*

In order to get a preliminary view on efficacy and safety results, an interim analysis is planned once the first 16 subjects will have completed 12 weeks of treatment and the follow-up visit (or have discontinued earlier). The interim analysis will be limited to the primary efficacy endpoint, DEXA parameters and safety data. At the time of the interim analysis, the interim analysis subjects' treatment arm will be unblinded. All other subjects will remain blinded.

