Sampling for pharmacokinetic assessments ^h			X	X	X	X	
Sampling for pharmacodynamic assessments ^{h,i}		X	X	X	X	X	X
Hot Flashes Severity and Frequency ^j		X	X	X	X	X	X
Hot Flash Related Daily Interference Scale ^k			X	X	X	X	X
Leeds Sleep Evaluation Questionnaire ^l			X	X	X	X	X
Greene Climacteric Scale ^l			X	X	X	X	X
Sheehan Disability Scale ^l			X	X	X	X	X
Clinical laboratory tests and urinalysis ^m		X	X	X	X	X	X
Bone density markers ⁿ			X			X	
Vital signs ^o		X	X	X	X	X	X
ECG ^p		X	X	X		X	X
Randomization			X				
ePRO training		X					
Dispensing of study drug ^q			X	X	X		
Intake of study drug ^r			X	X	X	X	
Compliance ^s				X	X	X	
Concomitant therapies ^t		X	X	X	X	X	X
Adverse events ^t		X	X	X	X	X	X

Footnotes on the next page.

- a. All visits need to be planned in the morning, fasted (for unbiased glucose, insulin, and C-peptide determination). Visit 2 should be planned to allow for first intake of study drugs at the clinical site, between 7:00 and 10:00 AM. For each subject, all visits during the treatment period subsequent to Visit 2 should be planned at the same time of the day, in the morning. A deviation of ± 1 day is allowed on the visits during the treatment period subsequent to the first study drug intake (Visits 3-5).
- b. Screening is to be performed within 4 weeks prior to the first intake of study drug, with a minimum of 7 days to allow for baseline data collection of Hot Flash Score and Hot Flash Frequency.
- c. Two to 3 weeks after the last intake of study drug.
- d. No study-related assessments are to be carried out before signing of the informed consent form.
- e. Includes height, weight, and waist circumference (height at screening only).
- f. Includes HBsAg, and anti-HCV and HIV antibodies.
- g. For practical reasons, the timing of DEXA may vary from the actual time of the visit, depending on DEXA availability (DEXA appointment). The Visit 2 DEXA can be performed prior to Visit 2 during the screening period, as well as at Visit 2 but must be performed before randomization. The Visit 5 DEXA can be performed ± 4 days from the actual time of Visit 5. It is however to be performed before the last dose of the study drug; in case the DEXA appointment related to Visit 5 is scheduled later in time than Visit 5, study drug intake must be continued until DEXA has been performed.
- h. Predose at Visits 2, 3, and 4; predose and 3 hours postdose at Visit 5.

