Collection of hot flashes severity and frequency will be started on an ad hoc basis, but at a minimum twice-daily (morning and evening), via ePRO diary. Data on hot flash severity and frequency collected during the screening period will serve as baseline for Hot Flash Score and Hot Flash Frequency.

An overview of the assessments to be performed at the screening visit is provided in the [Time and Events Schedule](#).

Adverse events and concomitant therapies will be collected from signing of informed consent onwards (screening) through the follow-up visit.

All results from the screening procedure that are needed to evaluate eligibility, including the clinical laboratory results, must be available prior to randomization (Visit 2). Any abnormal assessment at the screening visit will be assessed according to its clinical relevance, and if found relevant, the subject will not be included in the study.

Unscheduled visits may be planned to assess, confirm, and follow-up on an out-of-range clinical laboratory test, vital sign, or ECG value that will determine a subject's eligibility, or in case of a positive urine drug screen. Results of this retest must be available prior to randomization. The result of the retest will be considered for subject eligibility. Findings made during unscheduled visits should be reported in the source documents and in the designated sections of the eCRF.

For screening failures, demographic data, the date of screening and signature of the ICF, and the reason(s) for screening failure will be recorded on the eCRF.

7.1.2 *Treatment Period (Visits 2-5; Weeks 1-12)*

Visit 2 should be scheduled in the morning between 7:00 and 10:00 AM, fasted. In- and exclusion criteria will be reassessed. Eligible subjects will be randomized in a 1:1 ratio to one of the 2 treatment arms (ESN364 90 mg b.i.d. or placebo). Predose assessments for efficacy (questionnaires), PK (ESN364 plasma concentrations), PD (hormone concentrations), and safety (clinical laboratory testing, bone density marker concentrations, vital signs, ECG, and physical examination) parameters will be made to serve as baseline (except for Hot Flash Score and Hot Flash Frequency, for which baseline will be data collected during the screening period).

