7.5 SAFETY EVALUATIONS

Safety evaluation in this study will be based on AEs, clinical laboratory tests, plasma bone density marker concentrations, ECG, vital signs, and physical examination, as described in the following sections.

7.5.1 *Safety Variables*

7.5.1.1 *ADVERSE EVENTS*

Adverse events will be monitored continuously from informed consent until the last study-related activity. At regular intervals during the study, subjects will be asked non-leading questions to determine the occurrence of any AEs. All AEs reported spontaneously during the course of the study will be recorded as well.

For detailed definitions and reporting procedures of AEs, see [Section 10](#).

7.5.1.2 *CLINICAL LABORATORY TESTS*

Blood and urine samples will be collected at the time points indicated in the [Time and Events Schedule](#).

Blood samples will be collected and handled as specified in the central laboratory manual. Biochemistry and hematology testing will be performed on these samples, as well as coagulation and serology (HbsAg, anti-HCV and HIV antibodies) on the sample from screening. All blood samples for clinical laboratory tests should be taken in a fasted state (overnight fast for at least 10 hours; intake of water will be allowed until one hour before study drug intake) for unbiased glucose, insulin, and C-peptide determination.

Standard laboratory tests will be performed by the central laboratory BARC (Gent, Belgium). Further procedures for sample collection, shipment, processing, and storage are described in the laboratory manual provided by the central laboratory.

The following clinical laboratory tests will be performed on the samples:

- Biochemistry: sodium, potassium, uric acid, creatinine, calcium, AST, ALT, urea, alkaline phosphatase (ALP), gamma glutamylaminotransferase (GGT), albumin, glucose (fasted for at least 10 hours) total bilirubin (and direct bilirubin in case $>1.3 \times \text{ULN}$), creatine kinase (CK), and total protein;
- Coagulation: international normalized ratio (INR), activated partial thromboplastin time (aPTT) (at screening only);
- Hematology: white blood cell (WBC) count with differential (neutrophils, lymphocytes, eosinophils, monocytes, basophils), hemoglobin, hematocrit, red blood cell (RBC) count, platelet count.

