8.2 REMOVAL OF SUBJECTS FROM THE STUDY OR TREATMENT

Subjects have the right to withdraw from the study at any time for any reason, including personal reasons. A subject can withdraw without giving a reason. This will not affect the subject's future care. The Investigator should however try to find out why a subject has withdrawn from the study and document the reason for withdrawal in the source documents and on the eCRF.

A subjects **may** be withdrawn from the study or treatment in the event of:

- An AE, including clinically significant new or worsening existing conditions as judged by the Investigator (documented on the AE Form of the eCRF);
- Subject request (subject moved, schedule conflicts, etc);
- A major protocol violation which would confound interpretation of the results;
- Other: this reason should only be used if the reason for withdrawal is not better accounted for by one of the other categories.

A subjects **must** be withdrawn the study or treatment in the event of:

- Withdrawal of informed consent;
- Lost to follow-up;
- For safety reasons, it being in the best interest of the subject that she be withdrawn, in the Investigator's opinion;
- Development of a medical condition that requires concomitant treatment with a prohibited therapy (see Section [6.2](#));
- Breaking of the randomization code during administration of the study drug by the Investigator or by a member of his/her staff. If the code is broken by the Sponsor, for safety reporting purposes, the subject may remain in the study.
- QT interval corrected according to Fridericia's formula (QTcF) increases to >500 ms, as confirmed by 2 additional ECG recordings obtained within 10 minutes of the initial recording;
- Confirmed decrease in thrombocytes below 75.000, which does not normalize after 7 days;
- ALT or AST >8x ULN;
- ALT or AST >5x ULN for more than 2 weeks;
- ALT or AST >3x ULN and total bilirubin >2x ULN;
- ALT or AST >3xULN with the appearance of fatigue, nausea, vomiting, right upper quadrant pain or tenderness, fever, rash, and/or eosinophilia (>5%).

See [Attachment 6](#) for the procedure to follow in case of suspected drug-induced liver injury (DILI).

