10. ADVERSE EVENT REPORTING

10.1 DEFINITIONS

Adverse Event

An AE is any untoward medical occurrence in a clinical study subject administered a medicinal (investigational or non-investigational) product. An AE does not necessarily have a causal relationship with the study drug. An AE can therefore be any unfavorable and unintended sign (including an abnormal finding), symptom, or disease temporally associated with the use of a medicinal (investigational or non-investigational) product, whether or not related to that medicinal (investigational or non-investigational) product.

This includes any occurrence that is new in onset or aggravated in severity or frequency from the baseline condition, or abnormal result of diagnostic procedures, including clinical laboratory test abnormalities.

Serious Adverse Event

An SAE is any untoward medical occurrence that at any dose meets any of the following conditions:

- results in death;
- is life-threatening, i.e., the subject was at risk of death at the time of the event (e.g., ventricular fibrillation and anaphylaxis). The term does not refer to an event which hypothetically might have caused death if it were more severe.
- requires inpatient hospitalization or prolongation of existing inpatient hospitalization:
Hospitalization refers to an overnight admission into hospital for the purpose of investigating and/or treating the AE. Hospitalization for an elective procedure, or routinely scheduled treatment for a pre-existing condition that has not worsened, is not an SAE.
- results in persistent or significant disability/incapacity, i.e., causing substantial disruption of the subject's ability to conduct normal life;
- is a congenital anomaly/birth defect;
- is medically significant, i.e., may not be immediately life-threatening or result in death or hospitalization but may jeopardize the subject's health or may require intervention to prevent one of the above outcomes. Examples of such events are intensive treatment in an emergency room or at home for allergic bronchospasm, blood dyscrasias, or convulsions that does not result in hospitalization or development of drug dependency or drug abuse.

Unlisted (Unexpected) Adverse Event

An AE is considered unlisted if the nature or severity is not consistent with the applicable product reference safety information (see Investigator's Brochure [\[14\]](#)).

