10.6 RECORDING OF ADVERSE EVENTS

All (S)AEs occurring during the clinical investigation must be documented in the source documents and on the AE forms of the eCRF.

Whenever possible, diagnoses should be given when signs and symptoms are due to a common etiology (e.g., cough, runny nose, sneezing, sore throat, and head congestion should be reported as “upper respiratory infection”). Investigators must record their opinion concerning the relationship of the (S)AE to the study drug in the source documents and on the eCRF. All measures required for (S)AE management must be recorded in the source documents and reported according to Sponsor’s instructions.

All AEs occurring at any time during the study (including the follow-up period) will be followed by the Investigator until satisfactory resolution (e.g., value back to baseline value) or stabilization or until final database lock. If necessary, in order to obtain additional information to ensure safety to the subject, additional blood and urine samples may be taken at the discretion of the Investigator. Certain long-term AEs related to therapy cannot be followed until resolution within the setting of this study. In these cases follow-up will be the responsibility of the treating physician.

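### Section 9.1.5 defines treatment-emergent AEs by start date with no clause for worsening, so an AE open from screening that worsens on study drug drops out of the by-arm table if the site only raises its grade

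*Protocol*

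**What the plan says.** **Analysis rule.** Protocol Section 9.1.5 states: "The reported AEs will be allocated to phases based on their start date". It then states: "All AEs with onset during the treatment phase (i.e., TEAEs) will be summarized by treatment arm", broken down by System Organ Class and Preferred Term. All AEs are listed whatever their phase. Summaries or narratives for subjects with severe or serious AEs, or with discontinuation because of an AE, are optional.

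**Definition of an AE.** Section 10.1 says: "This includes any occurrence that is new in onset or aggravated in severity or frequency from the baseline condition". Section 8.2, in its list of reasons for withdrawal, also treats worsening of an existing condition as an AE to be documented on the AE form.

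**Collection window.** Sections 7.1.1 and 7.1.2 say: "Adverse events and concomitant therapies will be collected from signing of informed consent onwards (screening) through the follow-up visit". On the length of the pre-dose window, footnote b of the Time and Events Schedule says: "Screening is to be performed within 4 weeks prior to the first intake of study drug, with a minimum of 7 days".

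**Endpoint.** Section 7.5.2 defines the AE endpoint as frequency and severity, counted from first dose.

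**Recording.** Section 10.2 requires a severity grade for each AE. Section 10.6 says: "All (S)AEs occurring during the clinical investigation must be documented in the source documents and on the AE forms of the eCRF". Neither says what a site should do when an AE that is already open changes grade.

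**The concern.** AE records can be open on Day 1, because collection begins at consent. If such an AE gets worse on study drug, the worsening is an AE under Section 10.1 and belongs to the endpoint in Section 7.5.2. Whether it reaches the by-arm table depends on its start date, since that is the only criterion in Section 9.1.5. The protocol fixes that criterion without fixing which start date a worsening receives.

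Two things are at stake. Worsening after first dose is a possible drug effect, and under one way of recording it the planned comparison between arms does not contain it. And because the trial is multicenter, the same clinical course could count at one site and not at another. An endpoint that includes severity should not depend on local form-filling habits.

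**Working it through.** The protocol gives no figure on this point to reproduce. The check sets the sections side by side, followed by a short calculation of scale.

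**Step 1. Can an AE be open at first dose?** Yes. Collection starts at consent, and screening takes place between 7 days and 4 weeks before first dose (Sections 7.1.1 and 7.5.1.1; Time and Events Schedule, footnote b).

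**Step 2. What makes an AE treatment-emergent?** Only onset in the treatment phase, judged by start date (Section 9.1.5). The definition is introduced with an i.e., so it is given as complete, and it contains no worsening clause.

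**Step 3. Is worsening an AE?** Yes, under Section 10.1, with support from Section 8.2.

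**Step 4. What start date does the worsening get?** Take an AE that starts in screening at Grade 1 and rises to Grade 2 during treatment.
- *Case A: the site opens a new record dated at the worsening.* The start date is in the treatment phase. The event is a TEAE and enters the by-arm table.
- *Case B: the site raises the grade on the existing record.* The start date stays in screening. The event is not a TEAE, is absent from the by-arm table, and appears only in the listing.

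Sections 10.1 and 8.2 are compatible with Case A, since they treat worsening as an AE. Other parts of Section 10 fit Case B at least as well. Section 10.6 has every AE followed until it resolves or stabilises (or until database lock), which suggests one continuing record. Section 10.2 asks for a severity rating per AE. The outcome list in Section 10.5 has no entry for an AE that worsened and was re-entered. No section chooses between the cases.

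**Step 5. Scale.** There are 40 subjects per arm, so one subject missed is 1/40 = 2.5 percentage points of an arm's incidence. The documents give neither the share of subjects with an AE open at first dose nor the share of those who worsen. For illustration only, assume 10% to 30% for the first and 5% to 15% for the second, across all 80 subjects:
- low: 80 × 0.10 × 0.05 = 0.4 subjects
- high: 80 × 0.30 × 0.15 = 3.6 subjects

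These are totals over both arms and apply only if every such worsening is recorded as in Case B. With Case A throughout, the number is zero.

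**The case against.** The best reply is that the sections can be read together. If aggravation is an AE in its own right, it begins when the aggravation begins. An aggravation after first dose then has its onset in the treatment phase and is a TEAE under Section 9.1.5 as written. This stands as a possible reading, and it rules out saying that worsened screening AEs are certainly excluded. It does not settle the matter, because nothing tells a site that an AE already open needs a second record.

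A second reply is that the answer may lie in documents not shown. Section 12.7 promises eCRF completion booklets, and Section 9.1 leaves statistical detail to the SAP. A booklet could indeed settle the recording question. The TEAE definition is different, because the protocol states it outright. Section 9.1.4 expressly defers the rules for valid diary days to the SAP, and Section 9.1.5 makes no such deferral here. A SAP that added worsening would depart from the protocol's text.

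A third reply is that nothing vanishes from reporting: all AEs are listed, and severe or serious AEs get special attention. That is correct and limits the harm. But a listing does not compare the arms, the additional summaries are only optional, and a change from mild to moderate is not covered by them.

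**Conclusion.** The point holds in conditional form. Section 9.1.5 defines TEAEs by start date alone, and the protocol does not say how worsening of an AE open from screening is recorded. If it is recorded as a change of grade, the on-treatment worsening is lost from the only by-arm AE table the protocol commits to, and sites may differ. The number of subjects is probably small. The range of 0.4 to 3.6 rests wholly on assumed rates and is not an estimate from the documents.

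Two stronger readings are tempting and are not supported:
- *That such AEs are always left out.* This needs Case B, which no section states.
- *That the table is biased toward no difference, with headache as the example.* The 7 of 18 women with headache in Section 1.5 is a count of side effects on ESN364, not a rate before dosing. The documents give no pre-dose prevalence of headache and no sign that losses would be larger in the active arm.

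This is a matter of a better definition at very low cost. It does not threaten the trial's safety conclusions.

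**What to change.** Two changes:
1. In Section 9.1.5, define a TEAE as an AE with onset on or after first dose, or with onset before first dose and an increase in severity or frequency on or after first dose.
2. In Section 10.6, state that when an AE open from before first dose worsens on or after first dose, the worsening is entered as a new AE dated at the worsening. Repeat this in the eCRF completion instructions.

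Both are needed. If a record carries only one grade, the wider definition cannot be programmed, because the grade at first dose is not known. The recording rule alone would leave the definition in Section 9.1.5 silent on worsening.

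The cost is a small amount of extra programming and site instruction, with no new assessments or visits. It is best done before sites have settled into different habits.
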